3.2.2. Secondary Endpoints

- The baseline-adjusted mean change in the CPA at 1 year as determined by digital morphometric analysis of liver biopsies
- Proportion of subjects who have at least one stage change in Ishak histopathological staging of fibrosis at 1 year as assessed on liver biopsy
- The baseline-adjusted mean change in liver stiffness as determined by FibroScan[®] (if available) score prior to the first infusion, at Infusion Visit 13, and 14 to 28 days after final infusion
- The baseline-adjusted mean change in the metabolic capacity of the liver as determined by cPDR₃₀ of the MBT (if available) at screening, Infusion Visit 13, and 14 to 28 days after final infusion
- Proportion of subjects who have at least one stage change in Brunt-Kleiner histopathological staging of fibrosis at 1 year as assessed on liver biopsy

- The difference between GR-MD-02-treated and placebo-treated subjects in the progression of cirrhosis at 1 year, defined as the development of any of the following:
 - esophageal variceal hemorrhage or portal hypertensive gastropathy hemorrhage (confirmed by endoscopy or interventional radiology)
 - clinically apparent ascites
 - spontaneous bacterial peritonitis
 - overt hepatic encephalopathy
 - an increase from baseline in Child-Turcotte-Pugh Score ≥ 2 points
 - newly diagnosed varices in a subject without prior varices
 - progression from small to medium or large varices
 - qualification for liver transplant defined as a MELD score ≥ 15
 - listing for a liver transplant or the performance of a liver transplant
 - liver-related mortality

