8.1.1. Primary Analysis

The primary efficacy endpoint, change from baseline in HVPG at 1 year (53 to 55 weeks), will be analyzed using analysis of covariance (ANCOVA) with baseline values taken as a covariate using the FAS population at a significant level of 0.05 (2-sided). Treatment effect will be evaluated as a contrast of each active treatment versus placebo and described using continuous summary. To control the type I error rate due to multiple comparisons, the Bonferoni-Holm (1988) procedure for the comparison between treatment group and control will be implemented. Estimate of mean difference along with 95% CI will also be presented.

Missing HVPG at 1 year will be imputed using the last observation carried forward (LOCF) method. The sensitivity analysis will be performed on the change from baseline in HVPG based on the LOCF values in the FAS population using the same statistical methodology described above.

Additional sensitivity analyses for HVPG will include:

- Change from baseline in HVPG at 1 year in the MITT population.
- Change from baseline in HVPG at 1 year in the PP population.

The following subgroup analysis will also be conducted in the MITT population:

- Change from baseline in HVPG at 1 year by baseline HVPG category of MPH and CSPH
- Change from baseline in HVPG at 1 year by gender.
- Percentage of subjects who have $\geq 10\%$ and $\geq 20\%$ decrease at 1 Year in HVPG by baseline HVPG category of MPH and CSPH
- Percentage of subjects with HVPG at CSPH level at Baseline and at MPH level at 1 Year

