8.2. Key Secondary Efficacy Endpoints

There are six key secondary efficacy endpoints: CPA, Ishak histopathological stage, FibroScan[®], MBT, Brunt-Kleiner histopathological stage and complications of cirrhosis.

CPA

CPA will be used to measure liver collagen (a surrogate for fibrosis) by evaluation of liver biopsy at screening and 14 to 28 days after final dose (53 to 55 weeks). A single experienced pathologist, [name] (INNOVA Medical Center), will evaluate all liver biopsies at a central pathology laboratory.

The CPA will be summarized for the FAS population by visit and treatment group, for all scheduled visits, along with the change from baseline descriptively in a summary table and graphically.

Ishak histopathological stage

Fibrosis will be evaluated by liver biopsy and be staged according to the Ishak histopathological stage (0-6) at screening and 14 to 28 days after final dose (53 to 55 weeks). The number and percentage of subjects by Ishak histopathological stage will be summarized using the FAS population by treatment group. The number and percentage of subjects changing in Ishak histopathological stages will also be presented.

FibroScan[®]

FibroScan[®] will be only performed at the study centers where it is available and used to evaluate liver stiffness which is recorded as the pressure measurement of kPa at the scheduled visits.

The FibroScan[®] (if available) will be summarized for the FAS population by visit and treatment group, for all scheduled visits, along with the change from baseline descriptively in a summary table and graphically.

MBT

The MBT will only be performed at the study centers where it is approved. The cumulative percentage dose recovery of the metabolized ¹³C-methacetin 30 minutes after ingestion of the test substrate will be used as the MBT parameter for this study. Delta over baseline (DOB) with corresponding time point (T_n) will be collected on the eCRF.

The $cPDR_{30}$ is defined as:

$$cPDR_{30} = \frac{\frac{T_1}{60} \cdot PDR_1}{2} + \sum_{i=2}^n \frac{\frac{T_i - T_{i-1}}{60} \cdot (PDR_i + PDR_{i-1})}{2}$$

where $PDR_i = 1.817853 \times DOB_i \times w^{0.5378} \times h^{0.3963}$, $w = weight$ (kg), $h = height$ (cm).

Brunt-Kleiner histopathological stage

Fibrosis will be evaluated by liver biopsy and be staged according to the Brunt-Kleiner histopathological stage (0-4) at screening and 14 to 28 days after final dose (53 to 55 weeks).

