The number and percentage of subjects by Brunt-Kleiner histopathological stage will be summarized using the FAS population by treatment group. The number and percentage of subjects changing in Brunt-Kleiner histopathological stages will also be presented.

Complications of cirrhosis

Complications of cirrhosis with portal hypertension is defined as the development of any of the following:

- esophageal variceal hemorrhage or portal hypertensive gastropathy hemorrhage (confirmed by endoscopy or interventional radiology)
- clinically apparent ascites
- spontaneous bacterial peritonitis
- overt hepatic encephalopathy
- an increase in Child-Turcotte-Pugh Score ≥ 2 points
- newly diagnosed varices in a subject without prior varices
- progression from small to medium or large varices
- qualification for liver transplant defined as a MELD score ≥ 15
- listing for a liver transplant or the performance of a liver transplant
- liver-related mortality

The incidence of complications will be summarized in a table with count and percentage of subjects by each complication event using the FAS population by treatment group. Subjects with any complication event will also be presented.

In addition, Child-Turcotte-Pugh score and MELD score will be summarized descriptively at the scheduled visits. Child-Turcotte-Pugh class and MELD score (<15 , ≥ 15) will also be summarized.

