8.2.1. Key Secondary Efficacy Analysis

The 6 key secondary efficacy endpoints will be examined using a gatekeeper statistical approach and will be tested sequentially in the order of 1) CPA, 2) FibroScan[®], 3) Ishak histopathological stage, 4) MBT, 5) Brunt-Kleiner histopathological stage, 6) complications of cirrhosis. Analysis of the secondary endpoints will be conducted if the primary endpoint is significant ($\alpha < 0.05$). If a secondary endpoint does not meet statistical significance, then all the subsequent secondary endpoints will be treated as exploratory.

CPA

The change from baseline in CPA at 1 year (53 to 55 weeks), will be analyzed using robust regression (M estimation method, Huber 1973) using the FAS population at a significant level of 0.05 (2-sided). Treatment effect will be evaluated as a contrast of each active treatment versus placebo and described using continuous summary.

Sensitivity analyses for CPA will include:

- Change from baseline in CPA at 1 year will be analyzed based on the LOCF values using the FAS population.
- Change from baseline in CPA at 1 year will be analyzed using the MITT population.
- Change from baseline in CPA at 1 year will be analyzed using the PP population.

Ishak histopathological stage

The proportion of subjects who have at least one stage change in Ishak histopathological staging of fibrosis at 1 year will be analyzed using the FAS population. Fisher Exact Test will be used to compare the difference between treatment groups.

Sensitivity analyses for Ishak histopathological stage will include:

- The proportion of subjects who have at least one stage change in Ishak histopathological staging of fibrosis at 1 year will be analyzed using the MITT population.
- The proportion of subjects who have at least one stage change in Ishak histopathological staging of fibrosis at 1 year will be analyzed using the PP population.

FibroScan[®]

The change from baseline in FibroScan[®] (if available) at 1 year will be analogous to the primary efficacy endpoint, using the ANCOVA model for the FAS population. The baseline value of FibroScan[®] (if available) will be used as a continuous covariate in the ANCOVA model.

Sensitivity analyses for FibroScan[®] (if available) will include:

- Change from baseline in FibroScan[®] (if available) at 1 year will be analyzed based on the LOCF values using the FAS population.

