- Change from baseline in FibroScan[®] (if available) at 1 year will be analyzed using the MITT population.
- Change from baseline in FibroScan[®] (if available) at 1 year will be analyzed using the PP population.
- Treatment effect for FibroScan[®] (if available) overtime will be estimated using a mixed model repeated measures (MMRM) analysis with the FAS population.

MBT

The change from baseline in MBT (if available) at 1 year will be analogous to the primary efficacy endpoint, using the ANCOVA model using the FAS population. The baseline MBT will be used as a continuous covariate in the ANCOVA model.

Sensitivity analyses for MBT (if available) will include:

- Change from baseline in MBT (if available) at 1 year will be analyzed based on the LOCF values using the FAS population.
- Change from baseline in MBT (if available) at 1 year will be analyzed using the MITT population.
- Change from baseline in MBT (if available) at 1 year will be analyzed using the PP population.
- Treatment effect for MBT (if available) overtime will be estimated using MMRM analysis with the FAS population.

Brunt-Kleiner histopathological stage

The proportion of subjects who have at least one stage change in Brunt-Kleiner histopathological staging of fibrosis at 1 year will be analyzed using the FAS population. Fisher Exact Test will be used to compare the difference between treatment groups.

Sensitivity analyses for Brunt-Kleiner histopathological stage will include:

- The proportion of subjects who have at least one stage change in Brunt-Kleiner histopathological staging of fibrosis at 1 year will be analyzed using the MITT population.
- The proportion of subjects who have at least one stage change in Brunt-Kleiner histopathological staging of fibrosis at 1 year will be analyzed using the PP population.

Complications of cirrhosis

The incidence of complications of cirrhosis with portal hypertension at 1 year will be analyzed using the FAS population. A standard chi-square test will be used to compare the incidence of complications of cirrhosis between treatment groups.

Sensitivity analyses for complications of cirrhosis will include:

- The incidence of complications of cirrhosis with portal hypertension at 1 year will be analyzed using the MITT population.
- The incidence of complications of cirrhosis with portal hypertension at 1 year will be analyzed using the PP population.

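### The Ishak and Brunt-Kleiner key secondary endpoints count a stage change in either direction, so the gatekept Fisher tests pool improvers with worseners

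*SAP*

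**What the plan says.** SAP 3.2.2 lists as a secondary endpoint: "Proportion of subjects who have at least one stage change in Ishak histopathological staging of fibrosis at 1 year as assessed on liver biopsy". SAP 8.2.1 repeats this for the analysis ("The proportion of subjects who have at least one stage change in Ishak histopathological staging of fibrosis at 1 year") and for its MITT and PP sensitivity analyses. The Brunt-Kleiner endpoint is parallel: "The proportion of subjects who have at least one stage change in Brunt-Kleiner histopathological staging of fibrosis at 1 year". The test for each is stated as follows: "Fisher Exact Test will be used to compare the difference between treatment groups". It names neither a direction nor the dose comparison that must succeed.

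The descriptive text in SAP 8.2 is equally neutral: "The number and percentage of subjects changing in Ishak histopathological stages will also be presented" and "The number and percentage of subjects changing in Brunt-Kleiner histopathological stages will also be presented". The objectives in SAP 2.2 refer only to change in staging.

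Both endpoints are in the gatekept sequence, Ishak third and Brunt-Kleiner fifth of six. The rule for a failed step is: "If a secondary endpoint does not meet statistical significance, then all the subsequent secondary endpoints will be treated as exploratory".

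Elsewhere the SAP does give a direction. The HVPG responder analyses in 8.1.1 require a "decrease at 1 Year in HVPG by baseline HVPG category of MPH and CSPH", and the Child-Turcotte-Pugh component of cirrhosis progression in 3.2.2 requires a rise from baseline. For staging, direction appears only in the SAP Addendum of 26 January 2018, item 2 under secondary endpoints. There an ordinal model uses Decrease, No Change and Increase, with Decrease as the event level. The addendum describes its analyses as post hoc.

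**The concern.** An undirected event measures how much staging moved, not whether it improved. Two consequences follow.

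- **A benefit can be hidden.** If active treatment produces more improvers and fewer worseners, the two differences offset each other in the count of changers. A drug that helps in both directions can show no difference at all.
- **A significant result is ambiguous.** More changers on active may mean more improvement or more worsening. Fewer changers on active may mean less worsening or less improvement.

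Because Ishak is third in the sequence, a missed benefit makes MBT, Brunt-Kleiner and complications of cirrhosis exploratory. A pass that does not reflect benefit opens the way to them. Improvement was probably what the authors meant, but a confirmatory step should not depend on the programmer's reading.

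**Working it through.** **Inputs from the documents.** There are 52 subjects per arm with 25% dropout (SAP 4.1), which leaves 52 × 0.75 = 39 evaluable. Tests are two-sided at 0.05 (SAP 4). Ishak runs 0–6 and Brunt-Kleiner 0–4 (SAP 8.2). Entry is at Ishak 5 or 6 in SAP 3.1, and at Ishak 4, 5 or 6 in protocol 4.1.1.

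**The plan's own figure.** The 52 per arm is sized for HVPG only. With a difference of 2 and an SD of 3 mm Hg, 80% power needs 37 per arm by t-test, and 37 / 0.75 rounds up to 50, which is close to 52. No sizing is given for either staging endpoint.

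**Assumed.** The documents give no stage-change rates and no baseline stage mix, so all rates below are illustrations. One active arm is compared with placebo.

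**A single data set.** Suppose active has 12 improvers and 4 worseners of 39, and placebo has 4 improvers and 12 worseners of 39.
- As written: 12 + 4 = 16 of 39 against 4 + 12 = 16 of 39, Fisher p = 1.0.
- Decrease-only: 12 of 39 against 4 of 39, Fisher p = 0.047.

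**Power.** Let A and P be the event probabilities on active and placebo. Power is the sum of Bin(i; 39, A) × Bin(j; 39, P) over all pairs (i, j) whose two-sided Fisher p is at most 0.05. For the written endpoint the event probability is improve + worsen; for decrease-only it is improve. The ordinal column is an exact permutation rank-sum test with midranks on Decrease / No Change / Increase.

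| Active improve/worsen v placebo improve/worsen (%) | As written | Decrease-only | Ordinal |
|---|---|---|---|
| 30/0 v 10/0 (no worsening) | 51.9% | 51.9% | 51.9% |
| 30/10 v 10/10 (equal worsening) | 39.4% | 51.9% | 41.9% |
| 30/10 v 10/20 | 9.9% | 51.9% | 61.7% |
| 30/10 v 10/30 (exact cancellation, 40 v 40) | 2.8% | 51.9% | 80.4% |
| 10/10 v 10/30 (drug only prevents worsening) | 39.4% | 1.6% | 41.9% |
| 10/30 v 10/10 (harm) | 39.4% | 1.6% | 41.9% |

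Rows 2 and 6 have the same event rates under the written definition, 40% v 20%, so that test cannot tell them apart. In both, nearly all significant results have more changers on active. The ordinal test also reaches significance 41.9% of the time under harm, but it favours active in only 0.01%.

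**Ceiling.** Subjects at the top stage cannot worsen. Apply 10% v 30% worsening only to those who can, keeping improvement at 30% v 10%:

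| Share at top stage | Worsening overall | As written | Decrease-only | Ordinal |
|---|---|---|---|---|
| Half at Ishak 6 | 5% v 15% | 10.7% | 51.9% | 69.5% |
| Three quarters at Ishak 6 | 2.5% v 7.5% | 25.2% | 51.9% | 63.1% |
| 90% at Brunt-Kleiner 4 | 1% v 3% | 39.6% | 51.9% | 57.4% |

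**All 52 per arm evaluable** (as written / decrease-only): equal worsening 52.4% / 66.5%; exact cancellation 3.5% / 66.5%; prevention of worsening only 52.4% / 1.9%.

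**The case against.** The strongest reply concerns reach. Ishak is tested only after HVPG, CPA and FibroScan have all succeeded, and the powers above are not conditioned on that. Harm on staging read as benefit, after three favourable results including CPA from the same biopsies, is remote. Stages and stage changes are tabulated by arm, so a reader could largely see which way each arm moved. This stands, and it limits the severity, but tabulation does not change the test that decides the sequence.

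Second, the largest losses need placebo to worsen two or three times as often as active within a year, and nothing in the documents supports those rates. The planning assumption for placebo is no mean change in HVPG (protocol 7.6), though that is a different measure. This also stands: with equal worsening the loss is 51.9% to 39.4%, and with no worsening it is nil.

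Third, if nearly all subjects start at Brunt-Kleiner stage 4, the two definitions nearly coincide there. The point is therefore mainly about Ishak.

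Fourth, the protocol supplied is the original of February 2015, and the SAP differs from it in places, such as Ishak eligibility. The protocol's secondary endpoints (7.2) include neither staging endpoint and so give no direction. A later version might, but the SAP governs the analysis and should state the direction itself.

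Finally, neither remedy is better in every case. That is true, and the choice between them is a design decision. It is not a reason to leave the event undirected.

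**Conclusion.** The point holds. Following the SAP exactly pools improvement with worsening in two gatekept confirmatory tests. The wording is certain; the practical effect is not, because every rate used here is assumed. Under those rates the power lost relative to a decrease-only event runs from none (no worsening), through 12.5 points (51.9 − 39.4, equal worsening), to 49.1 points (51.9 − 2.8, exact cancellation, the extreme case). Independently of power, a significant result under the written definition does not identify benefit. This should be fixed, but it does not threaten the trial: the primary analysis and sample size are unaffected.

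**What to change.** Before unblinding, state the direction for both endpoints in SAP 3.2.2, 8.2 and 8.2.1, by one of two routes.

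1. **Simplest.** Define the event as a decrease of at least one stage, keep the Fisher test, and report the proportion with an increase of at least one stage separately by arm. The drawback is that it would not detect a drug that only prevents worsening (1.6% in the case above).
2. **Ordinal.** Prespecify a Decrease / No Change / Increase comparison, the classification already used in the addendum. It uses movement in both directions, but has less power than decrease-only when worsening is equal in the arms (41.9% against 51.9%).

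Under either route, say that these two steps pass only on a significant result favouring active treatment, and name the dose comparison that must succeed.

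The cost is SAP wording. The biopsies and the reader stay the same; route 1 keeps the test and route 2 replaces it with one ordinal test. If the data have already been unblinded, the definition can no longer be changed as a confirmatory one. Improvement and worsening should then be reported separately by arm beside the planned test and labelled post hoc.

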## 7.6 Sample Size Calculations

A total of approximately 156 subjects will be enrolled in the study. Sample size calculations are based on the comparison of the primary efficacy variable, change in HVPG from baseline, with the following assumptions (key assumptions discussed as follows):

1. True mean change in HVPG from baseline at 52 weeks in the placebo group,  $\Delta p = 0$
2. True mean change in HVPG from baseline at 52 weeks in either GR-MD-02 dose group,  $\Delta G = -2$  mm Hg
3. Common SD for difference in HVPG,  $\sigma = 3$  mm Hg
4. Null hypothesis,  $H_0: \theta = G - \Delta p = 0$
5. Type I error,  $\alpha = 0.05$  (2-sided significance test)
6. Power = 80%
7. Statistical test = 2-sample  $t$ -test for mean difference
8. Randomization ratio = 1:1:1
9. Drop-out rate of 25%

For a mean difference of 2 mm Hg and accounting for a 25% dropout rate, the total sample size of 156 subjects ( $n = 52$  subjects per group) will be required to achieve power of 80% with a 2-sided type I error rate of 0.05.

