3.2.5. PK Endpoint

The PK endpoints include plasma concentrations and population PK parameters of GR-MD-02.

The population PK analysis will be described in a separate modeling analysis plan.

4. General Statistical Considerations

Study day for events on or after the date of the first infusion will be defined as the number of days from the date of the first infusion of IMP, plus 1 day, so that the date of the first

infusion will be defined as Day 1. For events before the date of the first infusion, study day will be calculated as the difference in days between the date of the first infusion and the date of interest. Thus, the day before the date of the first infusion will be defined as Day -1. This means there will be no study day zero (0).

Baseline is defined as the last assessment prior to the first infusion of IMP. All baseline measurements must have been collected prior to administration of first infusion of IMP. Measurements that are obtained after the first infusion of IMP will be considered as post-baseline values. If the measurement of a variable is not made on a given subject prior to the first infusion of IMP, then that subject will be considered not to have a baseline value for that variable. Change from baseline is defined as post-baseline assessment minus baseline assessment.

Continuous data will be described using the following descriptive statistics: the number of subjects (n), mean, standard deviation (SD), median, the first quartile (Q1), the third quartile (Q3), minimum and maximum, where appropriate. Categorical data will be summarized using the frequency count (n) and percentage (%) of subjects for each category, where appropriate.

Unless otherwise specified, all statistical tests and confident intervals (CIs) will be two-sided and conducted at the 0.05 significance level. If analysis variables are not normally distributed, Poisson-regression model (or the negative binomial) will be applied for counts data.

No imputation will be applied for missing data unless otherwise specified.

All collected data used for safety and efficacy evaluations will be presented in listings. Data will be displayed in all listings sorted by treatment group and subject identifier unless specified otherwise.

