4.1. Sample Size

The sample size of 52 subjects per treatment arm assumes a mean difference in the change of HVPG from baseline at 52 weeks between an active treatment arm and placebo of 2 mm Hg with a SD of 3 mm Hg, and allows for a 25% dropout rate and 80% power to detect a statistically significant difference at an α level of 0.05. A difference of 2 mm Hg in the change of HVPG is considered to be of “clinical significance” (Villanueva 2009; Escorsell 2000; Abraldes 2003). The SD of 3 mm Hg at a mean change of HVPG of 2 mm Hg from baseline is based on primary data, obtained from an investigator ([name]), as reported in a published longitudinal clinical study (Groszmann 2005).

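### The gated FibroScan and MBT tests leave some Visit 13 data unused; gating on the MMRM would be a cheap gain in precision and robustness to dropout

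*SAP*

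**What the plan says.** SAP 8.2.1 tests six key secondary endpoints in sequence: CPA, FibroScan, Ishak stage, MBT, Brunt-Kleiner stage, complications of cirrhosis. Once one fails, the rest are exploratory.

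For FibroScan, the change from baseline "at 1 year will be analogous to the primary efficacy endpoint, using the ANCOVA model for the FAS population". MBT has the parallel sentence. SAP Section 4 sets the default: "No imputation will be applied for missing data unless otherwise specified". For both endpoints, LOCF appears only in the list of sensitivity analyses. So does the repeated-measures model: the FibroScan treatment effect "overtime will be estimated using a mixed model repeated measures (MMRM) analysis with the FAS population", and "Treatment effect for MBT (if available) overtime will be estimated using MMRM analysis with the FAS population".

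Both measures are scheduled before treatment, at Infusion Visit 13 (Week 25), and 14 to 28 days after the last infusion (SAP 3.2.2; Protocol 6.1.3.7 and Table 12-2). HVPG and liver biopsy have no mid-study value. Protocol 7.9.2 ties the FibroScan and MBT analyses to the method used for the primary endpoint. SAP 3.1 asks for a FibroScan and an MBT at a follow-up visit in early terminators where possible, but does not say whether these count as 1-year values.

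**The concern.** The single-visit ANCOVA suits HVPG, which has one post-baseline measurement. FibroScan and MBT have two. A subject who leaves after Visit 13 and has no later value contributes nothing to the gated test, although the Visit 13 result says something about where that subject was heading.

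Two things could follow: a larger standard error than necessary, and bias if the subjects who leave differ at Visit 13 from those who stay. Disease-related departure is plausible here. Protocol 4.2.1 lists clinically significant laboratory changes and intercurrent illness as withdrawal reasons, Protocol 5.9 has subjects who need a prohibited medication discontinued, and a footnote to Table 12-2 foresees termination after a clinical event.

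The sequence is decided by the ANCOVA. A FibroScan miss makes four later endpoints exploratory and an MBT miss makes two. The sensitivity MMRM could show a discrepancy but could not change that outcome.

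**Working it through.** **The plan's own figure.** Protocol 7.6 sizes the trial on HVPG: "For a mean difference of 2 mm Hg and accounting for a 25% dropout rate", 52 per group are required "to achieve power of 80% with a 2-sided type I error rate of 0.05", with an SD of 3 mm Hg and a two-sample t-test. The exact t calculation gives 37 evaluable per arm, and 37 / 0.75 = 49.3, so 50. That is within two of the stated 52. With 52 × 0.75 = 39 evaluable, power is 82.8% by the t-test (83.7% by the normal approximation). No size or power is given for FibroScan or MBT, so only the 25% allowance and the 39 of 52 are carried forward, as assumptions.

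**Precision.** Take two post-baseline visits, monotone dropout, an unstructured covariance and visit-specific baseline effects. Then

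Var(MMRM) / Var(ANCOVA) = 1 − r²(1 − p),

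where r is the Visit 13 to 1-year correlation given baseline, and p is the share of subjects with a Visit 13 value who also have a 1-year value. The documents give no r, so a range is shown. With 25% dropout in all:
- half of it after Visit 13: p = 0.75 / 0.875 = 0.857, so 1 − p = 0.143;
- all of it after Visit 13: p = 0.75, so 1 − p = 0.25.

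| r | Half after Visit 13: variance ratio | SE reduction | All after Visit 13: variance ratio | SE reduction |
|---|---|---|---|---|
| 0.3 | 0.987 | 0.6% | 0.978 | 1.1% |
| 0.5 | 0.964 | 1.8% | 0.938 | 3.2% |
| 0.7 | 0.930 | 3.6% | 0.878 | 6.3% |
| 0.8 | 0.909 | 4.7% | 0.840 | 8.3% |

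Effective size per arm rises from 39 to between 39 / 0.987 = 39.5 and 39 / 0.840 = 46.4. For an illustrative effect of 0.667 SD, power (normal approximation) rises from 83.7% to between 84.2% and 89.5%.

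**Bias.** Simulation: 52 per arm, 25% dropout, all after Visit 13, 6,000 replicates. Where dropout depends on Visit 13 it is logistic with slope 1 per SD, and worse values leave more often. Lower values are better, as for FibroScan; for MBT the signs reverse. Bias is in SD units. Monte Carlo error is about 0.225 / √6000 = 0.003.

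| Dependence on Visit 13 | True effect, Visit 13 / 1 year | ANCOVA bias, r = 0.5 / 0.7 | MMRM bias, r = 0.5 / 0.7 |
|---|---|---|---|
| None | 0 / 0 | 0.002 / −0.005 | 0.001 / −0.006 |
| None | −0.4 / −0.667 | −0.002 / −0.001 | −0.001 / −0.001 |
| Same in both arms | 0 / 0 | −0.004 / 0.006 | −0.006 / 0.005 |
| Same in both arms | −0.4 / −0.667 | 0.024 / 0.036 | −0.001 / 0.001 |
| Same in both arms | −0.667 / −0.667 | 0.038 / 0.057 | −0.004 / 0.000 |
| Placebo only | 0 / 0 | 0.108 / 0.152 | 0.001 / 0.003 |
| Placebo only | −0.4 / −0.667 | 0.104 / 0.156 | −0.003 / 0.005 |
| Active only | 0 / 0 | −0.101 / −0.151 | 0.004 / −0.001 |

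Against an ANCOVA standard error of √(2/39) = 0.226 SD, the common-mechanism bias is 0.024 / 0.226 = 0.11 to 0.057 / 0.226 = 0.25 of a standard error. The arm-differential bias is 0.101 / 0.226 = 0.45 to 0.156 / 0.226 = 0.69. Further simulations under similar assumptions gave 0.01 to 0.03 SD for a common mechanism with a treatment effect, and 0.09 to 0.17 SD for an arm-differential one.

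**The case against.** The strongest reply is that the plan already covers this. MMRM and LOCF are both prespecified for both endpoints, both use Visit 13, and a discrepancy would be visible. Only the choice of gated analysis is open, the SAP follows Protocol 7.9.2 in making it, and the primary conclusion is untouched. That is fair as to scale. It does not answer the point that the gate itself rests on the analysis using less of the data.

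Three stronger readings are tempting and are not supported:

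- **That dropout related to Visit 13 biases the result as such.** It does not. Under a mechanism common to the arms and no treatment effect the bias is zero, so that mechanism adds no false-positive risk. With a treatment effect the bias is small and conservative. The larger figures need a mechanism that differs by arm, and nothing in the documents shows that one will operate.
- **That the gated tests use completers only.** SAP 3.1 and Protocol 4.2.2 and 6.1.4 seek end-of-study values in subjects who stop early. The accurate statement is that the tests use subjects with a 1-year value, and that the mapping of early-termination values is unstated. The LOCF sentence for HVPG in SAP 8.1.1 is also unclear, but the separate listing of LOCF as a sensitivity analysis for FibroScan and MBT supports the observed-case reading.
- **That exchanging the two analyses costs nothing.** The main SAP gives no MMRM terms, covariance structure or 1-year contrast. Terms appear only in the post-hoc addendum, for other measures.

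**Conclusion.** The point holds in a limited form: this is a cheap improvement, not an error that undermines the trial. Gating FibroScan and MBT on the ANCOVA gives up roughly 1% to 5% in standard error if half of a 25% dropout follows Visit 13, and at most about 8% if all does. It leaves the contrast open to a bias of about 0.01 to 0.06 SD toward the null under a common mechanism with a treatment effect, or about 0.1 to 0.17 SD, in either direction and also under the null, if the mechanism differs by arm. The MMRM stayed within 0.01 SD of the truth in every setting tabulated.

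These sizes rest on assumptions outside the documents: r between 0.3 and 0.8, the timing of dropout, a logistic slope of 1 per SD, and dropout that depends only on observed values. The 25% is the allowance made for HVPG, not a forecast for these measures. Limited site availability lowers the sample size but not the relative gain.

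**What to change.** In SAP 8.2.1, make the gated test for FibroScan and for MBT the treatment contrast at Weeks 53-55 from an MMRM in the FAS. Its terms should be baseline, treatment, visit, treatment-by-visit and baseline-by-visit, with an unstructured covariance. State the degrees-of-freedom method. State how FibroScan and MBT values from early-termination visits map to the scheduled visits. Keep the observed-case ANCOVA as a sensitivity analysis.

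The cost is small. No new data are needed, and with two post-baseline visits the unstructured covariance has only three parameters. The MMRM must be written out in full, and the SAP should record the change from Protocol 7.9.2, which ties these two endpoints to the primary endpoint's method. The change belongs in the plan before unblinding.
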